# **The effects of isokinetic exercises on muscle strength, joint position sense, and kinesiophobia in patients with multiple sclerosis: a randomized controlled trial**

## **ABSTRACT**

**Objective:** To evaluate the effects of isokinetic exercises on muscle strength, knee joint position sense, pain, kinesiophobia, and quality of life in patients with multiple sclerosis.

**Design:** Randomized controlled trial.

**Setting:** Outpatient clinic.

**Participants:** Sixty patients with multiple sclerosis.

**Interventions:** Fifty patients were randomized to an isokinetic exercise (n:25) or home exercise programme (n:25).

**Outcome measures:** The outcome measures were the peak torque/body mass index of quadriceps and hamstring muscles at 60°/s and 180°/s velocities, the hamstring/quadriceps ratios at the same velocities, absolute angular errors of the 15°, 45°, and 60° and the mean absolute angular error of joint position sense of the less and more affected knees, and the scores of Multiple Sclerosis Quality of Life-54, Visual Analogue Scale, and Tampa Scale of Kinesiophobia.

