## **INTRODUCTION**

In one study, the muscle strength of the quadriceps and hamstring, which were tested with the isokinetic muscle strength test, were found to be lower in patients with multiple sclerosis (MS) than the controls (1). In another study, bilateral muscle strength of the quadriceps and hamstring were shown to be related with walking speed, balance, and functional capacity (2). Therefore, the authors concluded that muscle strengthening exercises for the quadriceps and hamstring should be included in the rehabilitation program of MS patients.

It is known that slowing afferent proprioceptive conduction and impaired central integration of the proprioception are the main causes of balance deficit in MS patients. Proprioception impairment, often seen in patients with MS, negatively affects the joint position sense (JPS), balance, and posture. Joint repositioning, muscle strengthening,

plyometric, balance, coordination and vibration exercises are recommended to improve JPS, proprioception, and balance in this patient group (3).

It has been reported that exercise training improves and/or maintains functional capacity, strength, endurance, fatigue, quality of life (QoL), depression, cognition, and chronic disease risk factors among MS patients. The current evidence suggests that exercise training is generally safe for MS patients and not associated with an increased relapse risk. Resistance and endurance training modalities are the major types of exercises in MS patients (4).

There are not enough studies on isokinetic muscle strengthening exercises in MS patients with muscle weakness. Robineau et al. (5) and Aubry et al. (6) reported that isokinetic knee flexion-extension exercises improved quadriceps and hamstring muscle strength and control of the knee in this patient group. Manca et al. (7) investigated the efficiency of isokinetic ankle dorsiflexor training, and the muscle strength of ankle dorsiflexors improved significantly in MS patients.

Kinesiophobia is defined as “an excessive, irrational and debilitating fear of physical movement and activity resulting from a feeling of vulnerability to painful injury or reinjury” and is related with the disability level (8). MS patients show fear avoidance beliefs and behaviors which are related with pain. Although catastrophizing and fear avoidance beliefs and behaviors have been reported in MS patients, they have not been investigated in detail (9).

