To the best of our knowledge, no study has explored the effects of isokinetic training on knee JPS, pain, kinesiophobia, and QoL in MS patients. Therefore, in the current study, we aimed to observe the knee JPS and kinesiophobia level, their relationships with QoL, and the effects of isokinetic exercises on these variables.

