### **Procedure**

Fifty patients were randomized to two groups: isokinetic exercise (Group 1) (n=25) and home exercise (Group 2) (n=25). Randomization was completed using sequentially numbered, opaque envelopes by the investigator. All patients gave informed consent before the assessment. The outcome measures were assed initially and at eighth week after the treatment. Group 1 performed isokinetic concentric quadriceps and hamstring strengthening exercises under supervision and Group 2 performed lower extremity muscle strengthening and balance exercises at home.

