#### **Muscle strength and JPS testing**

Muscle strength and knee JPS were tested by an isokinetic dynamometer (Biodex System 3 Pro Multijoint). Before muscle strength and knee JPS testing, the patients were informed about the procedure. First knee JPS was tested, and then muscle strength was measured. The machine was calibrated before the procedure. Before muscle strength testing, the patients performed quadriceps and hamstring stretching exercises and on-site counting for five minutes for warming-up. The seat angle was set to 85° and the patient was asked to sit down. Appropriate parts for knee testing were placed in the dynamometer. The lateral femoral condyle, which is the rotation axis of the knee, was aligned to the rotation axis of the dynamometer. The patients were stabilized by thoracic, pelvic and thigh belts. The patient's leg was bound to the leverage equipment from the upper part of the medial malleolus. During

the test, the patients were asked to place their arms sideways. After determining the range of motion and gravity correction for the mass of the limb, the patients performed three submaximal warm-up contractions at 60°/s angular velocity. After warming up, the patients rested for 10 seconds, and then performed five maximal concentric knee flexion-extension at 60°/s and 10 maximal concentric knee flexion-extension at 180°/s angular velocities, separated by 20 seconds of seated static recovery. Both the more and less affected legs were tested in order, two minutes after the seated static recovery period. During the test, the quadriceps and hamstring peak torque (PT), the peak torque (PT)/body mass index (BMI), and the hamstrings/quadriceps (H/Q) ratio were evaluated at 60°/s and 180°/s angular velocities in Newton/meter (N/m) (10).

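### The objective credits isokinetic exercise, but the trial compares a supervised isokinetic programme with an unsupervised home strengthening and balance programme, so no outcome can isolate the isokinetic mode

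*Combined protocol and SAP*

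**What the plan says.** The title is "The effects of isokinetic exercises on muscle strength, joint position sense, and kinesiophobia in patients with multiple sclerosis: a randomized controlled trial". The objective in the Abstract is "To evaluate the effects of isokinetic exercises on muscle strength, knee joint position sense, pain, kinesiophobia, and quality of life". The aim at the end of the Introduction is worded in the same way: "we aimed to observe the knee JPS and kinesiophobia level, their relationships with QoL, and the effects of isokinetic exercises on these variables". None of the three names a comparator. The Interventions line of the Abstract does name both arms, but only as isokinetic exercise and a home exercise programme.

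The Methods describe the arms more fully. Under Isokinetic training program, Group 1 trains the quadriceps and hamstrings concentrically at 60°/s and 180°/s in two doctor-supervised sessions a week for eight weeks. Under Procedure, "Group 2 performed lower extremity muscle strengthening and balance exercises at home". Under Home exercise program, that is three unsupervised sessions a week for eight weeks, with two calls a week to ask about continuity and give encouragement.

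Strength is tested on an isokinetic dynamometer. Under Muscle strength and JPS testing, patients "performed five maximal concentric knee flexion-extension at 60°/s and 10 maximal concentric knee flexion-extension at 180°/s angular velocities". For the legs, "Both the more and less affected legs were tested in order".

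Statistical Analysis specifies a Mann-Whitney test between the groups, without naming outcomes. It also specifies Wilcoxon tests of before-after change within each group, and there it does name strength, knee JPS, kinesiophobia and QoL.

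**The concern.** The stated question concerns a type of exercise. The randomised question concerns two programmes that differ in type of exercise and in other ways. If the report keeps the wording of the objective, a between-group difference could be read as a property of isokinetic exercise when it may owe something to supervision, to frequency or to the different content.

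The wording can mislead in either direction:

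- A strength advantage in Group 1 could come from the isokinetic mode, from supervision, or from having practised the movement that is tested.
- A null result for JPS would not show that isokinetic training leaves JPS unchanged, because the comparator is itself active. The Introduction says that "plyometric, balance, coordination and vibration exercises are recommended to improve JPS, proprioception, and balance in this patient group", and balance work is described for Group 2 only.

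The within-group tests add to the risk. They are the only tests tied to named outcomes, so a significant before-after change in Group 1 could be presented as the effect of isokinetic exercise although nothing controls it.

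**Working it through.** The plan gives no sample-size, power or effect-size figure on this point, so there is none to reproduce. The check compares sections of the document and makes two simple counts.

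**1. The two arms side by side** (Procedure; Isokinetic training program; Home exercise program)

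| Feature | Group 1 | Group 2 |
|---|---|---|
| Exercise mode | Isokinetic, concentric, 60°/s and 180°/s | Lower-limb strengthening; mode, device and velocity not given |
| Supervision | A doctor, in person | None; two calls a week |
| Scheduled sessions | 2 × 8 = 16 | 3 × 8 = 24 |
| Balance exercises | None described | Yes |

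The calls come to 2 × 8 = 16 if they ran for all eight weeks. The number of scheduled contacts may therefore be equal, but a call about continuity is not supervised training.

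**2. What one contrast can identify.** For a given outcome, let Δ be the between-group difference. Even if the components simply add,

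Δ = (mode) + (supervision) + (frequency) + (balance content),

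where each term is Group 1 minus Group 2. Two arms supply one equation for four unknowns. Δ > 0 is compatible with a zero mode term. Δ = 0 is compatible with a positive mode term offset by the others. A larger sample estimates Δ more precisely but does not split it. Δ itself, the difference between the programmes as delivered, is identified by randomisation.

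**3. What the within-group test can identify.** The before-after change in Group 1 contains every term on the Group 1 side plus anything that would have changed over the period without the programme, including the effect of being tested a second time. The Wilcoxon test sets this total against zero, not against a control.

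**4. Test against training for strength.** The test is maximal concentric knee flexion-extension at 60°/s and 180°/s. Group 1 trains both muscle groups concentrically at the same two velocities. No such training is described for Group 2. For outcomes taken from this test, Δ therefore gains a fifth term, practice on the tested task.

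**5. How many outcomes come from that test.** The list is in the Abstract. Strength and JPS are counted for each leg, and the MSQoL-54 scores are those under Evaluation of quality of life:

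- PT/BMI: 2 muscles × 2 velocities × 2 legs = 8
- H/Q ratio: 2 velocities × 2 legs = 4
- JPS: (15°, 45°, 60°, mean) 4 × 2 legs = 8
- MSQoL-54: total, physical composite, emotional composite, pain = 4
- VAS = 1; TSK = 1

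The total is 8 + 4 + 8 + 4 + 1 + 1 = 26. PT/BMI and H/Q together are 8 + 4 = 12 of 26. The inseparability in step 2 applies to all 26, and the practice term in step 4 to these 12. JPS uses the same type of device but is an angle-reproduction task, so it is not counted.

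**6. Timing.** The plan says "The outcome measures were assed initially and at eighth week after the treatment". Whether this means the end of the programme or eight weeks after it, steps 2 to 5 are unchanged.

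**The case against.** The strongest reply is that nothing is hidden. The Abstract names both arms, the Methods state supervision, frequency and content openly, and short titles and objectives often name the experimental arm and leave the comparator to the Methods. Comparing two programmes is a legitimate question. The text reviewed contains no results or conclusions, so any misattribution is still only a risk. All of this stands. It means that the fault lies in the attribution and not in the randomised comparison. It does not remove the point, because the objective and aim are what a conclusion will answer, and the Abstract's arm labels mention neither doctor supervision nor balance work.

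On JPS, the same sentence of the Introduction also recommends muscle strengthening, which both arms receive, and a null result against any active comparator never shows that the experimental programme did nothing. That is fair. The balance content is one real difference between the arms, but the Introduction does not show that it outweighs the rest.

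A reader might go further and infer the following, which the documents do not support:

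- **That the strength comparison is biased towards Group 1 by a known or large amount.** The overlap shows exposure to the tested task, not a size of effect. For H/Q, where both muscles of the ratio are trained, even the direction is unclear.
- **That Group 2 did no concentric work.** Its exercises are not itemised, and ordinary strengthening may include it. What is firm is that no training at isokinetic velocities is described.
- **That Group 1 trained on the test machine.** The training section does not name its device. The match shown is of contraction mode and velocity.
- **That in-person contact explains differences in TSK, VAS or MSQoL-54.** It is a possible explanation, but no section supports it in particular.

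**Conclusion.** The point holds. The title, objective and aim attribute effects to isokinetic exercise, while the design can support only a statement about a supervised isokinetic programme against an unsupervised home strengthening and balance programme. This applies to every listed outcome and would remain at any sample size. For the 12 strength variables out of 26, practice on the tested task is a further inseparable explanation. The within-group Wilcoxon tests cannot establish an effect of either programme.

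The conclusion rests on the arm descriptions in the Methods and on the outcome count shown above, which treats each leg, muscle and velocity as a separate variable. It does not rest on any assumed effect of supervision, practice or content, and none can be computed from the documents. The randomised comparison of the two programmes as delivered remains valid. The wording and the role of the within-group tests should be changed, because this determines what the trial may conclude.

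**What to change.** 1. Word the objective, the aim in the Introduction and any conclusion as a comparison of a doctor-supervised isokinetic programme with an unsupervised home strengthening and balance programme. The title should be consistent with this.
2. In Statistical Analysis, state that every effectiveness claim rests on the between-group comparison, name each outcome to which that comparison applies, and label the within-group Wilcoxon tests as descriptive.
3. State that PT/BMI and H/Q are measured in the contraction mode and at the velocities that Group 1 trained, and that no effect specific to the isokinetic mode will be claimed from them.

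The cost is confined to wording and reporting. No outcome, assessment or exercise programme changes. The downside is a narrower claim, with nothing attributed to the isokinetic mode by itself.

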## **METHODS**

Following the Helsinki Declaration, the study was approved by the Ethics Committee of Ankara Training and Research Hospital, Health Sciences University (29.07.15, 603/5070). This prospective randomized controlled trial aimed to recruit 60 patients with MS from the physical medicine and rehabilitation clinic of Ankara Training and Research Hospital, Health Sciences University, Ankara, Turkey (June 2016 to June 2017).

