### **Participants**

Individuals were included if they had definite relapsing remitting MS and secondary progressive MS diagnosis, mild and moderate MS determined by Kurtzke Expanded Disability Status Scale (EDSS) scores below 6.5, and a disease duration of more than one year. The exclusion criteria were; having an acute exacerbation within the last three months, intravenous pulse steroid therapy in the last four weeks, grade 3-4 spasticity according to the Modified Ashworth Scale, severe vision impairment, severe fatigue and depression, past knee surgery, other neurologic diseases, systemic diseases, pregnancy, and having received an exercise program within the last four weeks. Fifty patients who met the inclusion criteria were enrolled in the study (Figure 1).

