## Statistical Analysis

The data were analyzed using the Statistical Package for the Social Sciences (SPSS) software version 15.0. The sample characteristics were summarized using descriptive statistics. Descriptive statistics tables were created for numerical variables, and frequency tables were constructed for categorical variables for both groups. The Kolmogorov-Smirnov test was used to test the normality of data. The Mann-Whitney U test was conducted to compare the two groups. The Wilcoxon test was performed for the comparison of before and after treatment values within the groups in terms of muscle strength, knee JPS, kinesiophobia, and QoL variables. The Spearman correlation test was utilized for the evaluation of relationships between muscle strength and knee JPS. The level of statistical significance was set at  $p<0.05$ .

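### Does the abstract misstate the sample size by listing sixty participants when fifty were randomised?

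*Combined protocol and SAP*

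**What the plan says.** The abstract gives two patient counts on consecutive lines. Under Participants it has "Sixty patients with multiple sclerosis". Under Interventions it has "Fifty patients were randomized to an isokinetic exercise (n:25) or home exercise programme (n:25".

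The body of the document gives three more:

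- Methods, opening paragraph: "This prospective randomized controlled trial aimed to recruit 60 patients with MS".
- Participants: "Fifty patients who met the inclusion criteria were enrolled in the study (Figure 1", with the reference to Figure 1 attached to that statement.
- Procedure: "Fifty patients were randomized to two groups: isokinetic exercise (Group 1) (n=25) and home exercise (Group 2) (n=25".

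The Statistical Analysis section names no sample size. It describes summaries by group, a Mann-Whitney comparison of the groups, Wilcoxon tests within groups and Spearman correlations. There is no power calculation, assumed effect, standard deviation or dropout allowance anywhere in the document.

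**The concern.** The Participants line of a structured abstract is where a reader, or someone extracting data for a systematic review, looks for the sample size. A bare number there is naturally taken as the number of patients in the trial. Here that number disagrees with the line directly below it and with two later sections.

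If sixty were meant as the trial's sample size, it would be ten too many. It might also raise the question of whether ten randomised patients had been left out, which would bear on the integrity of the comparison. That second possibility is what makes the discrepancy worth checking.

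**Working it through.** **Inputs**

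| Source | Count | How it is described |
|---|---|---|
| Abstract, Participants | 60 | no description |
| Abstract, Interventions | 50 (25 and 25) | randomised |
| Methods, opening paragraph | 60 | recruitment aim |
| Participants section | 50 | eligible and enrolled |
| Procedure section | 50 (25 and 25) | randomised |

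**Step 1: the plan's own sum.** 25 + 25 = 50. This reproduces the stated number randomised, so there is no arithmetic error.

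**Step 2: size of the gap.** 60 - 50 = 10. Relative to the number randomised this is 10/50 = 20.0%; relative to sixty it is 10/60 = 16.7%. Enrolment reached 50/60 = 83.3% of the aim. The 20.0% is an overstatement only if the Participants line was meant to report the number enrolled or randomised.

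**Step 3: what sixty could mean.**

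- *The recruitment aim.* This matches the Methods section exactly. The abstract would then have carried over the target without its label.
- *The number assessed for eligibility.* The Participants section ties the fifty to meeting the inclusion criteria, which fits a larger pool from which some were excluded. No available text says sixty were assessed, but Figure 1 is cited at just that point and was not available for this review, so its silence here proves nothing.
- *A target inflated for dropout.* 50/(1 - 1/6) = 60 works arithmetically, but the document states no dropout rate, so this cannot be credited.
- *A plain slip for fifty.* Possible, and corrected by the next line.

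Sixty randomised with ten dropped is the only reading that would harm the trial. The text contradicts it: enrolled and randomised counts agree at fifty wherever they are stated, and the arm sizes add up to that number.

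**Step 4: does anything depend on sixty?**

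- *Allocation:* 25 and 25.
- *Mann-Whitney tests:* at most 25 against 25.
- *Wilcoxon tests:* at most 25 pairs in each arm.
- *Spearman correlations:* no denominator is given. The natural one is the enrolled patients, at most 50, because the Procedure section describes assessment of the randomised patients.
- *Power:* no calculation exists, so none can be wrong on this account.

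Replacing or labelling the sixty changes none of these.

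**The case for a change.** The best case for a correction is that abstracts are often the only part read, that the number carries no label, and that the repair would be one line. Even if Figure 1 shows sixty assessed, a figure cited only in the body does not label the abstract's number. The correlations also have no stated denominator, so a stray sixty might be thought to leave some doubt about which patients enter them.

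Part of this stands. The line would be clearer with a label, and that need does not depend on what Figure 1 shows. Two things limit its force. First, the reader of the abstract meets the number randomised and both arm sizes in the very next line, so the misreading does not survive the abstract itself. Second, the missing denominator for the correlations is a separate matter from the abstract's wording. An analyst would use the patients measured and report the n, whatever the Participants line says.

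The stronger claim, that the line is wrong by 20.0%, does not stand. It assumes that sixty was meant as the number enrolled, which is the point in question.

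**Conclusion.** The inconsistency is real but clerical: an unlabelled sixty in the abstract beside a consistent fifty everywhere that enrolment or randomisation is described. The difference is ten patients. Its effect on allocation, the planned tests and the estimates is nil. Falling short of a recruitment aim is not an error, and the Methods section already labels its 60 as an aim.

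This rests on two assumptions: that the enrolled and randomised counts are correct as stated, which their agreement across three places supports, and that Figure 1 does not show more than fifty randomised. Whoever next edits the abstract may wish to say what the sixty refers to, in agreement with Figure 1, but nothing the trial does or concludes would alter, and no change to the plan follows.
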